#### **Data Analysis:**

For categorical variables, numbers and percentages of patients will be reported including the according 95% confidence intervals.

For continuous variables, mean, SD, minimum, first and third quartile (Q1, Q3), median, maximum and 95% confidence intervals will be calculated, together with the total number of observations and the number of missing values.

Descriptive statistics will summarize demographics and baseline characteristics.

The questionnaires scores will be calculated according to the algorithms elaborated for these questionnaires.

Visit windows will be defined only in the statistical analysis plan to group data in order to generate descriptive statistics across time to assess potential trends in PRO questionnaires, safety data, or CD4 cell count. P-values and confidence intervals (95% two-sided) will be calculated when considered relevant.

Multivariate logistic regression models will be used to model binary outcome variables (HIV-1 RNA suppression, categorical CD4 cell count, i.e., > 500, adherence and persistence of B/F/TAF).

Multivariate Poisson regression models will be used to model questionnaires scores (CCI [REDACTED]) and rates of AEs and SAEs.

Multivariate analyses will also be conducted to compare ART-naive and ART-experienced groups. Longitudinal analysis will be performed using mixed models.

Further details of the data analysis will be provided in the Statistical Analysis Plan.

Milestones:	EU PAS Registration	Q1 2018
	Start of data collection:	Q2 2018
	End of data collection:	Q3 2024
	Final report:	Q3 2025

---

This study will be conducted in accordance with the guidelines of Good Pharmacoepidemiology Practices (GPP) and Heads of Medicines Agencies (HMA) Good Pharmacovigilance Practices (GVP) including archiving of essential documents.

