## **7. RESEARCH METHODS**

### **7.1. Study Design**

This non-interventional study will be a prospective cohort comprised of HIV-1 infected adults who initiate B/F/TAF therapy in accordance with the approved summary of product characteristics (SmPC).

Patients can be enrolled in this study after the physician has independently decided to treat a specific patient with B/F/TAF and after patient's informed consent form (ICF) is obtained. Although the study will not define which therapy a patient will receive, only patients starting or switching to B/F/TAF will be enrolled.

Patient data will be collected prospectively according to clinical practice from initial enrollment into the study (Day 1/baseline) and thereafter (follow-up period) until study completion at Month 24 (or Month 60 for those patients entering the extension phase in Germany and France), lost to follow-up, withdrawal of consent, or death, whichever occurs sooner. Day 1/Baseline will be defined as the time at which patients either start (ART-naive) or switch to (ART-experienced) B/F/TAF.

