#### **7.1.1. Early Study Drug Discontinuation**

In case of B/F/TAF discontinuation, the date of discontinuation, reasons for discontinuation (eg, patient choice, adverse reaction, lack of efficacy) and patients' new ART will be collected. The patient will remain in the study and will be followed-up with the new ART until premature end of documentation (e.g., due to lost to follow-up) or until reaching the defined end of the study (24 months after enrollment). If the patient has subsequent changes in therapy, all ARV changes will be recorded until the patient completes the study.

For the extension phase of the study, applicable for patients in Germany and France: In case of B/F/TAF discontinuation in the extension phase, patients must be discontinued from the study with no further follow-up data being collected.

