#### **7.5. Study Size**

At least 1500 patients starting treatment with B/F/TAF (to include both ART-naive and ART-experienced patients) are planned to be enrolled into the study.

A sample size of 1500 patients will be appropriate to detect a proportion of HIV RNA suppression (< 50 copies/mL) of at least 90% with a power of 80% (Score z test: target proportion 90%, smallest detectable proportion 92.10%).

Additionally, assuming there are 30% of patients over age 50 years, then with 1050 patients < 50 years and 450 patients 50 years or older, there is more than 90% power to detect a difference in HIV RNA response rate between the age groups of at least 7%, assuming a 90% response rate in older patient (versus 83% in younger patients) and a two-sided alpha of 0.05 and a continuity corrected test of two proportions.

With a target of at least 200 patients per country, there is 80% power to determine a 7% difference in HIV RNA response rates between any country and the remaining countries, assuming a 90% response rate in the overall countries. In addition, assuming a 90% response rate in one country with 200 patients, there is more than 80% power to determine an 11% difference in HIV RNA response rates compared to any country including the same sample size.

The study will not have strict enrollment goals for specific strata of patient types. However, the protocol team will monitor enrollment into specific strata of interest (e.g., age > 50 years, treatment naive) and may close enrollment to a stratum in order to preserve statistical power to evaluate subgroups of interest.

Patients recruited in Germany, France and Canada (protocol ID: GS-CA-380-4574) will be included in the extension phase HIV RNA analysis. From the existing cohort of patients, a subsample of 400 patients will be appropriate to detect a proportion of HIV RNA suppression of at least 70% with a power of 80% (Score z test: target proportion 70%, smallest detectable

proportion 76.4%). A cumulative drop-out rate of 35% at Month 60 was applied to derive the projected Month 60 sample size.

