## **7.7. Data Analysis**

For categorical variables, numbers and percentages of patients will be reported including the according 95% confidence intervals.

For continuous variables, mean, SD, minimum, first and third quartile (Q1, Q3), median, maximum and 95% confidence intervals will be calculated, together with the total number of observations and the number of missing values.

Descriptive statistics will summarize demographics and baseline characteristics (including the type of regimen at enrolment). Once data is available from more than one country, descriptive analyses by country will be done to determine if patient heterogeneity exists across countries and sites.

The questionnaires scores will be calculated according to the algorithms elaborated for these questionnaires.

Visit windows will be defined in the Statistical Analysis Plan (SAP) to group data in order to generate descriptive statistics across time to assess potential trends in PRO questionnaires, safety data, or CD4. P-values and/or confidence intervals (95% two-sided) will be calculated when considered relevant.

Following descriptive analysis, a multiple imputation approach will be used to carry out multivariate analyses in case the assumptions of missing at random (MAR) are met. If this assumption doesn't hold, a complete case (subjects with all variables present) or regression approach may be used dependent on the results of a sensitivity analysis. Patterns of missing data

will be determined using the methodology outlined by Rubin {Rubin 1976}. Imputation methods will be used to account for missing values in the dataset adhering to current European Network of Centres for Pharmacoepidemiology and Pharmacovigilance (ENCePP) guidelines {European Medicines Agency 2010}.

Multivariate logistic regression models will be used to model binary outcome variables (HIV-1 RNA suppression, change in CD4 cell count category (e.g. CD4 > 500 at week 48), HIV RNA suppression, adherence and persistence of B/F/TAF).

Multivariate Poisson regression models will be used to model questionnaires scores (CCI ) and rates of adverse drug reactions (ADRs) and serious adverse drug reactions (SADRs), adjusted for confounding.

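### Persistence on B/F/TAF is modelled as a yes/no logistic outcome, which biases it modestly when patients are lost while still on drug; a time-to-discontinuation analysis would avoid this

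*Protocol*

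**What the plan says.** Section 7.7 (Data Analysis) states "Multivariate logistic regression models will be used to model binary outcome variables" and includes "adherence and persistence of B/F/TAF" in the list. The Data Analysis part of the synopsis makes the same choice. Neither place gives persistence a time point or says how a patient lost on drug is counted. The only longitudinal method named is mixed models; no survival method appears.

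The data have the form of event times with censoring:

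- **Stop dates.** Under Section 7.1.1, "the date of discontinuation, reasons for discontinuation" and the new regimen are recorded when B/F/TAF is stopped.
- **End of follow-up.** Section 7.1 collects data "until study completion at Month 24 (or Month 60 for those patients entering the extension phase in Germany and France), lost to follow-up". Death and withdrawn consent also end it.
- **After stopping, first 24 months.** "The patient will remain in the study and will be followed-up with the new ART" (Section 7.1.1).
- **After stopping, extension.** "patients must be discontinued from the study with no further follow-up data being collected" (Section 7.1.1).

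For missing data, Sections 7.7 and 7.9 plan multiple imputation for the multivariate analyses if data are missing at random. Otherwise a complete-case or regression approach may be used. The one stated attrition figure is in Section 7.5: "A cumulative drop-out rate of 35% at Month 60 was applied to derive the projected Month 60 sample size".

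**The concern.** A logistic model needs a yes or no at a chosen month. A patient who stops B/F/TAF has that answer from the day of stopping, whatever happens later. A patient who leaves while on drug has none: all that is known is that persistence lasted at least until then. Unknown outcomes therefore fall more often on patients who would have persisted than on those who would have stopped. This happens even if loss has nothing to do with stopping.

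Two things are at stake: the persistence percentage, and the odds ratios for its predictors. Sections 6 and 7.7 foresee comparisons of ART-naive with ART-experienced patients and between countries. If follow-up were less complete in one group, that group's persistence would look different for that reason alone.

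**Working it through.** **The plan's own figures.** None is given for persistence. The 35% belongs to the Month 60 HIV RNA calculation (400 patients, 70% against 76.4%, 80% power). That calculation reproduces: a one-sample score test at two-sided 0.05 (alpha assumed, as it is not stated there) has 81.6% power at 76.4%. It says nothing about persistence, so stopping and loss rates must be assumed.

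**Model (assumption).** Constant hazards of stopping and of loss, independent of each other. With S the true persistence and L the proportion that would be lost:

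- a = −ln(S), b = −ln(1 − L)
- still on drug and followed: N = S × (1 − L)
- seen to stop: E = a/(a + b) × (1 − N)
- lost on drug, outcome unknown: U = 1 − N − E
- persistence among known outcomes: N/(N + E)

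**Month 60, 20% stopping, 20% lost.** a = b = 0.223; N = 0.640; E = 0.5 × 0.360 = 0.180; U = 0.180. Known-outcome persistence = 0.640/0.820 = **78.0%**, true value 80.0%.

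**Month 24, 10% stopping, 20% lost.** a = 0.105, b = 0.223; N = 0.720; E = 0.321 × 0.280 = 0.090. Known-outcome persistence = 0.720/0.810 = **88.9%**, true value 90.0%.

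**Who is missing (20%/20%).** True persisters with unknown outcome: 0.80 × 0.20 = 0.16, which is 20% of the 0.80 who persist. True stoppers with unknown outcome: 0.18 − 0.16 = 0.02, which is 10% of the 0.20 who stop.

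- Imputation from baseline covariates alone gives the lost patients the persistence of the observed ones, so it returns about 78.0% again.
- Imputation that uses time on drug at loss assigns 0.16 of the 0.18 to persistence: 0.64 + 0.16 = 0.80, the true value.
- Censoring at loss also recovers 80.0% under these assumptions.

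**Range of known-outcome persistence.**

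| Assumed loss | True 90% | True 80% |
|---|---|---|
| 5% | 89.8% | 79.6% |
| 10% | 89.5% | 79.1% |
| 20% | 88.9% | 78.0% |
| 35% | 87.8% | 76.0% |

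The last row treats the whole 35% as loss, with stops on top. At 80% persistence that means a total exit of 1 − 0.80 × 0.65 = 48%. The 20%/20% case has a total exit of 1 − 0.80 × 0.80 = 36%, close to 35% if that figure counts stops as well as losses.

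**Group comparison.** Both groups have true persistence of 90%; loss is 35% in one and 20% in the other (assumed).

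- Odds on known outcomes: 0.585/0.0816 = 7.17 and 0.720/0.0898 = 8.02. Odds ratio 7.17/8.02 = **0.89**; the true value is 1.
- If lost patients were instead counted as stopped: (0.585/0.415)/(0.720/0.280) = 0.55.

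**The case against.** The strongest reply is that the protocol already has a route for missing outcomes, and that being on drug at a fixed month is a legitimate binary endpoint whose definition, time point and imputation model belong in the SAP. Much of this stands. A reader might infer that every lost patient must be dropped or called non-persistent; the imputation plan in Sections 7.7 and 7.9 shows otherwise. What does not stand is that imputation settles the matter by itself: it does so only if it uses time on drug at loss. The choice of logistic regression is made in the protocol and not left to the SAP.

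Three other stronger readings are tempting, and the document does not support them:

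- **That up to 35% of persistence outcomes are in doubt.** The 35% is a planning figure for the extension HIV RNA analysis. Because stopping ends participation in the extension, it may mix known stops with losses. No rate is given for the first 24 months.
- **That persistence would be understated by 16 to 18 points.** Counting every lost patient as stopped would give 64.0% (true 80.0%) or 72.0% (true 90.0%). The protocol neither states nor excludes that rule.
- **That the stop dates go unused, or that follow-up differs between groups.** Deriving status at a fixed month needs the date, and no differential loss is documented.

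Kaplan-Meier has its own condition: it recovers the true value above because loss was assumed independent of stopping.

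**Conclusion.** The point holds as a modest but avoidable flaw in a stated method. Persistence is event-time data with censoring, and the protocol commits it to a binary model in which missingness depends on the outcome. In the two scenarios worked through, the level is about 1 to 2 points too low. It would be 4 points too low at 80% persistence if 35% were lost in addition to those who stop. A comparison is distorted only if loss differs between groups; the 0.89 shows what one such difference would do. All of these sizes rest on assumed stopping and loss rates and on constant, independent hazards. Persistence is not among the visible primary or secondary objectives, and the primary result is untouched. The change is still worth making because the replacement is standard and uses data already planned.

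**What to change.** In Section 7.7 and in the Data Analysis part of the synopsis, take persistence off the logistic list and state instead:

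- The outcome is time from Day 1 to B/F/TAF discontinuation, with patients lost or withdrawn on drug censored at that point.
- Kaplan-Meier estimates are given at Months 12 and 24, and at Month 60 for the extension. Patients who do not enter the extension are censored at Month 24.
- Cox regression is used for predictors.
- Death on drug is a competing event, with the cumulative incidence of discontinuation reported on that basis.
- In the extension, exits because B/F/TAF was stopped count as events and are kept apart from losses.

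If a fixed-month binary version is kept, make it secondary. Name the month, say how patients lost on drug are counted, and put time on drug at loss into the imputation model.

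The cost is analysis wording and a little extra programming, since the discontinuation date is already collected. The downside is reliance on non-informative censoring, which should be stated as an assumption.

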## GLOSSARY OF ABBREVIATIONS AND DEFINITION OF TERMS

ABC	Abacavir
ADR	Adverse Drug Reaction
AE	Adverse Event
ART	Antiretroviral Therapy
ARV	antiretroviral
BfArM	The Federal Institute of Drugs and Medical Devices in Germany
BIC	Bictegravir
B/F/TAF	Bictegravir/ Emtricitabine/Tenofovir alafenamide
CD4	cluster determinant 4
CD8	cluster determinant 8
CDC	Centers for Disease Control and Prevention
CRF	Case Report Form
DTG	Dolutegravir
eCRF	Electronic Case Report Form
EDC	Electronic Data Capture
EMA	European Medicines Agency
FDC	Fixed Dose Combination
FTC; F	Emtricitabine
GLPS	Global Patient Safety
GPP	Good Pharmacoepidemiology Practices
GVP	Good Pharmacovigilance Practices
HIV	Human Immunodeficiency Virus
CCI	[REDACTED]
[REDACTED]	[REDACTED]
[REDACTED]	[REDACTED]
[REDACTED]	[REDACTED]
HMA	Heads of Medicines Agencies
HRQoL	Health Related Quality of Life
ICF	informed consent form
IEC	Independent Ethics Committee
INSTI	Integrase Strand-Transfer Inhibitor
MAH	Marketing Authorization Holder
MAR	missing at random
MCAR	missing completely at random
MICE	multiple imputation by chained equations
NRTI	Nucleoside Reverse Transcriptase Inhibitor
NtRTI	Nucleotide Reverse Transcriptase Inhibitor
PAS	Post-Authorization Study
PRO	patient reported outcome

PSMF	Pharmacovigilance System Master File
PVE	Pharmacovigilance and Epidemiology
Q1	first quartile
Q3	third quartile
QPPV	Qualified Person for Pharmacovigilance
RNA	ribonucleic acid
SADR	Serious Adverse Drug Reaction
SAE	Serious Adverse Event
SAP	Statistical Analysis Plan
SD	standard deviation
CCI	
SmPC	summary of product characteristics
SSR	Special Situation Report
TAF	tenofovir alafenamide (Vemlidy®)
TAFNES	Non-Interventional Real-Life Study of Effectiveness, Safety, Adherence, and Health-Related Quality of Life in Adult Patients receiving Elvitegravir/Cobicistat/Emtricitabine/Tenofovir alafenamide (E/C/F/TAF) or Emtricitabine/Tenofovir alafenamide (F/TAF) or Rilpivirine/Emtricitabine/Tenofovir alafenamide (R/F/TAF) for HIV-1 Infection in Germany
3TC	lamivudine
US, USA	United States, United States of America
VAS	visual analogue scale

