Two further ongoing phase 3 studies are evaluating B/F/TAF in virologically suppressed patients switching from an existing antiretroviral regimen containing either DTG (GS-US-380-1844) or a boosted protease inhibitor (GS-US-380-1878). In study GS-US-380-1878, switching to B/F/TAF was non-inferior to continuing a boosted darunavir- or atazanavir-based regimen with 92% versus 89% of patients achieving HIV-1 RNA < 50 copies/mL at 48 weeks and no patients treated with B/F/TAF developed resistance {[Daar 2017](#)}.

While large phase 3 clinical trials are fundamental to supporting the registration of new drugs, these studies are performed in highly selected patients under well controlled conditions. The results of such trials may be limited in terms of their generalizability to the wider HIV-infected population. Thus, there is a need for data derived from more heterogeneous patient populations, such as in observational cohorts, in order to help physicians gain a better understanding of the use of new drugs in real-life healthcare settings.

The aim of this non-interventional, multi-country, cohort study is to evaluate the effectiveness and safety of B/F/TAF in ART-naïve and ART-experienced HIV-1 infected adult patients as well as adherence, resource utilization, quality of life, health status, and treatment satisfaction during routine clinical practice.

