Multivariate analyses will be also conducted to compare treatment-naive and non-naive treatment groups. In order to maximize homogeneity between groups and reduce the impact of treatment-selection bias, an inverse probability of treatment weighted approach will be applied (Rosenbaum and Rubin 1983, Thoemmes and Ong 2016, {Austin 2011b} {Austin 2011a}). Demographics and baseline measures would be potential confounders/effect modifiers for multivariate analyses. Confounders/effect modifiers and respective adjustments will be addressed in the SAP. For multivariate analyses, significantly skewed data will be transformed using the fractional polynomial approach (Royston et al. 1999). Longitudinal analysis will be done using mixed models. Further details of the data analysis will be provided in the SAP.

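### Poisson regression is named for questionnaire scores with no robust variance or dispersion term, so model-based inference on patient-reported outcomes is miscalibrated unless the variance happens to equal the mean

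*Protocol*

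**What the plan says.** Protocol section 7.7 (Data Analysis) states: "Multivariate Poisson regression models will be used to model questionnaires scores". The same sentence covers rates of adverse drug reactions and serious adverse drug reactions. The Data Analysis part of the synopsis repeats the choice, there paired with rates of adverse events and serious adverse events.

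Other text that bears on the point:

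- Section 7.7 on how scores are formed: "The questionnaires scores will be calculated according to the algorithms elaborated for these questionnaires". The instrument names and the whole of section 7.3.2 are redacted.
- Section 5 gives the aims beyond effectiveness and safety as "adherence, resource utilization, quality of life, health status, and treatment satisfaction during routine clinical practice".
- The glossary contains an entry for a "visual analogue scale". This is the only visible hint of a scale type.
- Section 7.7 on inference: "P-values and/or confidence intervals (95% two-sided) will be calculated when considered relevant".
- Section 7.7 on repeated measurements: "Longitudinal analysis will be done using mixed models". No distribution or link is given.
- Section 7.7 on what is deferred: "Further details of the data analysis will be provided in the SAP".

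No visible text names a robust variance, an overdispersion parameter or any other regression model for the scores.

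**The concern.** A Poisson model ties the variance to the mean. That is a reasonable starting point for event counts observed over time. It has no such justification for a score built from rated items or marked on an analogue scale, where the spread is an empirical matter and is limited by the ends of the scale.

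The fitted mean may still be sensible. The standard errors are the weak part. If the variance exceeds the mean, they are too small, and differences between groups are declared too often. If the scores bunch near the top of the scale, they are too large, and real differences are missed.

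At stake are the adjusted comparisons of patient-reported outcomes, including any contrast of ART-naive with ART-experienced patients. Health-related quality of life is in the study title, so these results are likely to be reported and read.

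**Working it through.** The plan gives no figure for the questionnaire analysis, so there is nothing of its own to reproduce. **Every mean, SD and scale range below is an assumption.** The only input taken from the protocol is the 450/1050 split of 1500 patients used in the simulation, from section 7.5: "with 1050 patients < 50 years and 450 patients 50 years or older".

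**Formula.** Let φ = SD² / mean. The Poisson model sets φ = 1. The true standard error divided by the model-based one is then √φ, and a nominal two-sided 5% test has a real type I error of 2 × [1 − Φ(1.96 / √φ)].

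**One case in full.** Mean 80, SD 15 on 0-100: φ = 225 / 80 = 2.81; √φ = 1.68; 1.96 / 1.68 = 1.17; type I error 24.3%.

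**Range of cases.** The simulation drew rounded scaled-beta scores with no true difference between the groups, 4000 replicates per row.

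| Assumed scale | Mean, SD | φ | √φ | Type I error, formula | Type I error, simulated |
|---|---|---|---|---|---|
| 0-100 | 80, 10 | 1.25 | 1.12 | 8.0% | 8.2% |
| 0-100 | 80, 15 | 2.81 | 1.68 | 24.3% | 23.3% |
| 0-100 | 80, 20 | 5.00 | 2.24 | 38.1% | 38.1% |
| 0-60 | 45, 10 | 2.22 | 1.49 | 18.9% | 17.6% |
| 0-60, near ceiling | 54, 6 | 0.67 | 0.82 | 1.6% | 1.5% |
| 0-60, near ceiling | 56, 5 | 0.45 | 0.67 | 0.3% | 0.5% |
| 0-20 | 8, 5 | 3.12 | 1.77 | 26.8% | 26.1% |
| 0-20, variance = mean | 8, 2.83 | 1.00 | 1.00 | 5.0% | 4.8% |

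**Same data, robust variance.** Keeping the log-linear mean model and replacing the model-based standard error with a sandwich estimate brings the simulated type I error to between 4.6% and 5.3% in all eight rows.

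**Dependence on the unit.** Multiplying a score by 10 multiplies its variance by 100 and its mean by 10, so φ rises tenfold. The score with mean 80 and SD 15 on 0-100 has φ = 2.81. The same answers recorded on 0-10 have mean 8 and SD 1.5, so φ = 2.25 / 8 = 0.28, √φ = 0.53, and the type I error falls from 24.3% to about 0.02%. Nothing about the patients has changed.

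**Effect of adjustment.** The planned models are multivariable, so residual spread is what counts. Suppose covariates explain half the variance. For mean 80 and SD 15, φ = 112.5 / 80 = 1.41, √φ = 1.19, and the type I error is about 9.8% instead of 24.3%. For SD 20, φ = 200 / 80 = 2.5 and the error is about 21.5%. For SD 10, φ = 50 / 80 = 0.625 and the error is about 1.3%, now on the conservative side.

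**The case against.** The strongest reply has three parts.

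First, the instruments are hidden. A redacted parenthesis follows the word scores in both places and may list exactly which scores are meant. No visible text gives a range or type for any of them, and nothing links the analogue scale in the glossary to the Poisson model. A symptom-count score cannot be excluded. This stands: that these are scale scores is a strong inference from the constructs measured, not something the protocol states.

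Second, Poisson regression estimates a log-linear mean consistently if that mean is correctly specified, whatever the distribution. Only the model-based standard errors depend on the variance assumption, and the choice of variance estimator can be left to the SAP, which is not shown. This stands in part. The SAP could cure the problem with one sentence. But the protocol itself chooses the model family, shares it with event rates, and defers only further details.

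Third, the sizes are built on assumed means and SDs, and adjustment for covariates shrinks the residual variance. This stands, and the figures should be read as illustrations.

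A reader might also go further than the text allows in two ways:

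- *Change scores can be negative, so the model cannot be fitted.* No visible text applies Poisson regression to change scores. Longitudinal analysis is assigned to mixed models, and trends in the questionnaires are to be assessed descriptively by visit window.
- *Adherence results are affected.* Section 7.7 lists adherence among the binary outcomes for logistic regression.

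**Conclusion.** The point holds in a limited form. The protocol commits to a count model for questionnaire scores and names nothing to correct the variance. If that is followed with model-based standard errors, confidence intervals and p-values are miscalibrated unless variance equals mean, and they depend on the unit in which the score is recorded. The direction is not fixed: in the assumed cases the type I error of a nominal 5% test runs from about 8% to 38% for 0-100 scores with mean 80 and SD 10 to 20, and from about 0.3% to 1.6% for near-ceiling scores.

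It would be too strong to conclude that the questionnaire results will necessarily be wrong. A robust variance on the same mean model would make the inference valid, and the SAP may already require it.

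The primary endpoint, HIV-1 RNA suppression at Month 12, is unaffected. Patient-reported outcomes appear in the study aim but not among the visible primary or secondary objectives, and p-values or intervals are promised only where relevant. The change is worth making because the remedy is cheap, not because the main conclusion is at risk.

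**What to change.** In section 7.7 and in the synopsis, split the sentence so that scores and event rates are treated separately.

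- **Scores:** name a linear model, or a linear mixed model where measurements are repeated, adjusted for baseline score and with robust standard errors. State the distribution for the mixed models already planned.
- **If the log-linear Poisson mean model is kept for any score:** require sandwich standard errors as a minimum, and say why that mean model suits the instrument.
- **Poisson regression:** reserve it for event counts.

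The SAP should carry the same wording for each instrument. The cost is a text change in the protocol and SAP, with no new data, visits or patients.

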## 6. RESEARCH QUESTIONS AND OBJECTIVES

This non-interventional cohort study will evaluate the effectiveness, safety, adherence, resource utilization and PROs of B/F/TAF use in routine clinical care.

The primary objective of this study is:

- To evaluate HIV-1 RNA suppression, defined as HIV-1 RNA < 50 copies/mL, at 12 months after initiating or switching to B/F/TAF

The secondary objectives of this study are:

- To evaluate HIV-1 RNA suppression (<50 copies/mL) at Months 3, 6, and 24 for all patients after initiating or switching to B/F/TAF
- To evaluate changes in cluster determinant 4 (CD4) cell count and CD4/cluster determinant 8 (CD8) ratio at Months 3, 6, 12, and 24 for all patients after initiating or switching to B/F/TAF
- To assess rates of adverse events (AEs) and serious adverse events (SAEs)
- To evaluate the long-term effectiveness and safety of B/F/TAF in an extension phase through Month 60 in a subgroup of patients recruited in Germany and France:

To evaluate HIV-1 RNA suppression (< 50 copies/mL) at Months 36, 48, and 60 after initiating or switching to B/F/TAF

To evaluate changes in CD4 cell count and CD4/CD8 ratio at Months 36, 48, and 60 after initiating or switching to B/F/TAF

CCI [REDACTED]

- [REDACTED]
- [REDACTED]
- [REDACTED]
- [REDACTED]
- [REDACTED]

CCU [REDACTED]

[REDACTED]

[REDACTED]

The above parameters may be evaluated in various subgroups, e.g., ART-naive patients versus ART-experienced patients, by baseline viral load  $\geq$  or  $<$  100,000 copies/mL, age, presence of specific comorbidities, gender, as well as comparing between participating countries.

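### Poisson regression is named for adverse-event rates with no correction for variation between patients, so confidence intervals may be too narrow when events recur

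*Protocol*

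**What the plan says.** Section 7.7 (Data Analysis) names multivariate Poisson regression for questionnaire scores "and rates of adverse drug reactions (ADRs) and serious adverse drug reactions (SADRs), adjusted for confounding". The Data Analysis part of the synopsis (Section 2) names the same model family for questionnaire scores "and rates of AEs and SAEs". The two places therefore differ in outcome: causally related reactions in one, all adverse events in the other. Section 6 lists rates of AEs and SAEs as a secondary objective and allows the parameters to be examined by age, ART history, gender, comorbidity and country.

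Neither place gives an offset, a dispersion parameter or a variance estimator, and neither rules one out. Section 7.7 leaves further detail to the SAP. It assigns longitudinal analysis to mixed models without linking them to event rates. On inference it says only that "P-values and/or confidence intervals (95% two-sided) will be calculated when considered relevant".

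**The concern.** A patient can have several adverse events, and patients differ in how often they have them because of comorbidity, concomitant medication, reporting habits and site practice. Counts of all AEs per patient can then be expected to vary more than a Poisson distribution allows. If the heterogeneity is unrelated to the covariate, a Poisson model with a person-time offset still estimates the rate ratio properly, but its model-based standard errors are too small.

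At stake are the comparisons that Section 6 foresees. A difference in AE rate by age or country would be declared more often than the nominal 5%, and the 95% intervals would cover the true ratio less than 95% of the time.

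**Working it through.** **Inputs.**
- Model family: Poisson regression for event rates (Section 7.7 and synopsis).
- Study size, for illustration: 1500 patients. The 450/1050 split is the one in the age calculation in Section 7.5.
- Event rate and between-patient dispersion: not given. Assumed below, with ranges.
- The protocol states no precision or power for safety, so there is no figure of its own to reproduce.

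**Step 1: formula.** Let each patient's rate be gamma-distributed with a given shape, and let the mean count per patient be m. Then variance = m + m²/shape, so variance/mean = 1 + m/shape. The Poisson model assumes that this ratio is 1. With equal follow-up, the correct standard error of a log rate ratio exceeds the model-based one by the factor f = sqrt(1 + m/shape). The actual type I error of the nominal 5% Wald test is 2·Φ(−1.96/f). Neither depends on the number of patients, so a large study does not remove the problem.

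**Step 2: numbers with shape 1.**

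| Mean events per patient | f | Type I error, formula | Type I error, simulated |
|---|---|---|---|
| 0.1 | sqrt(1.1) = 1.05 | 6% | 5-7% |
| 1 | sqrt(2) = 1.41 | 17% | 16% |
| 2 | sqrt(3) = 1.73 | 26% | 25% |
| 4 | sqrt(5) = 2.24 | 38% | 39% |

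The simulation used 1500 runs per setting, 450 against 1050 patients, about 24 months of follow-up (shortened for 15% of patients) and no true difference. Patient-level robust variance brought the 16% at one event per patient back to 5%.

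**Step 3: other dispersions (formula).** At a mean of 1, shape 2 gives f = 1.22 and a type I error of 11%; shape 0.5 gives 1.73 and 26%. At a mean of 0.1, shape 0.5 gives 1.10 and about 7%; even shape 0.25 gives 1.18 and about 10%.

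**Step 4: coverage of the 95% interval.** A second simulation used 1500 patients, up to 2 years of follow-up, a log person-time offset, a binary covariate with no effect and 600 runs per setting. Here k = 1/shape.

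| Rate per person-year | k | Default Poisson | Robust variance |
|---|---|---|---|
| 0.05 | 0 | 96.2% | 95.8% |
| 0.05 | 1 | 92.8% | 94.0% |
| 0.05 | 2 | 93.2% | 94.7% |
| 0.5 | 0 | 95.0% | 94.7% |
| 0.5 | 1 | 84.7% | 95.3% |
| 0.5 | 2 | 74.7% | 95.7% |
| 2 | 0 | 94.8% | 94.7% |
| 2 | 1 | 62.5% | 93.7% |
| 2 | 2 | 50.0% | 95.3% |

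Simulation error at 95% coverage is sqrt(0.95 × 0.05/600), about 0.9 percentage points, so the robust column agrees with 95% throughout. Without heterogeneity (k = 0) the default interval is sound. With heterogeneity, its shortfall grows with the event rate.

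**The case against.** The strongest reply is that the protocol leaves this open. It does not say that the default variance will be used, and it does not exclude an offset, a scale parameter or robust variance. It refers detail to the SAP. Poisson regression with robust variance is still Poisson regression, so the SAP could add it without contradicting Section 7.7. This stands to the extent that a reader may not infer that the intervals are certain to be too narrow. It does not remove the point: the protocol chose the model family itself, for a secondary objective, and that model with its default variance is the one that fails. Moving to negative binomial regression in the SAP would also depart from the named model.

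Second, Section 7.7 speaks of ADRs and SADRs, a subset of all events that may be rare, and at low rates the distortion is small. That is correct. The larger figures apply to the AE rates named in the synopsis and in Section 6.

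Third, Section 7.7 plans inverse-probability weighting for ART-naive against ART-experienced patients, so an unweighted Wald test does not represent that comparison. This is also correct. The figures above bear on unweighted comparisons such as those by age or country. The mixed models do not settle the matter, because they are not assigned to event rates.

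**Conclusion.** The point holds conditionally. If event counts vary between patients beyond Poisson variation and the variance is not corrected, intervals for covariate effects on AE rates will be too narrow. With gamma heterogeneity of shape 1 they should be about 1.4 times wider at 1 AE per patient and 1.7 times wider at 2, with a type I error of about 17% and 26% instead of 5%. At 0.1 events per patient the error stays near 5-7%, so rare SAEs or SADRs are little affected. All these sizes rest on assumed rates and dispersion. It is a worthwhile correction to the analysis of a secondary objective; the primary endpoint is not involved.

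A reader might go further in two directions that the protocol does not support.

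- **Visit windows.** Visits are unequally spaced (gaps of 3, 3, 6 and then 12 months), and windows are to serve "to assess potential trends in PRO questionnaires, safety data, or CD4". One might infer that event counts will appear to rise simply because later windows are longer. But the protocol leaves the windows to the SAP, fixes no window lengths and does not say that raw event counts will be compared across them. The safety data meant may be laboratory values, which Section 7.3 schedules by visit, and the objective is worded as rates.
- **Extension countries.** One might infer that Germany and France, with follow-up to Month 60, will look safer. That needs event rates that fall over time and a pooled analysis of 24- and 60-month follow-up without a time term. The protocol gives neither, and only consenting patients enter the extension.

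**What to change.** In Section 7.7 and in the synopsis, state that adverse-event rates will be modelled by negative binomial regression, or by Poisson regression with patient-level robust variance, with log person-time as offset in either case. Because the two places name different outcomes (ADRs and SADRs against AEs and SAEs), the same edit should say which event sets the model covers.

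The cost is a sentence in each place and no new data. The downside is somewhat wider intervals where events recur: for a mean of 1 AE per patient and shape 1, about 1.4 times wider. If the SAP already specifies such a variance, the edit only aligns the protocol with it.
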